## List of Abbreviations

Term	Definition
ACPA	anti-citrullinated protein antibody
ACR	American College of Rheumatology
AE	adverse event
ALT	alanine aminotransferase
ANA	anti-nuclear antibody
ANC	absolute neutrophil count
anti-CCP	anti-cyclic citrullinated peptide
anti-CCP2	commercially available test for ACPA
AST	aspartate aminotransferase
BMS	Bristol-Myers Squibb
BP	blood pressure
C	Celsius
CBC	complete blood count
CRP	C-reactive protein
DIP	distal interphalangeal
DMARD	disease-modifying anti-rheumatic drug
dsDNA	double-stranded DNA
EDC	Electronic Data Capture
eg	exempli gratia (for example)
ET	early termination
F	Fahrenheit
FSH	follicle stimulating hormone
GCP	Good Clinical Practice
HR	heart rate
F	Fahrenheit
hsCRP	high-sensitivity C-reactive protein
INOVA	Inova Diagnostics
IP	investigational product
IRB	Institutional Review Board
kg	Kilogram
mg	Milligram
mL	Milliliter
MTX	Methotrexate
N	number of subjects or observations
N/A	not applicable
NIMP	non-investigational medicinal products
NSAID	nonsteroidal anti-inflammatory drug
NYU	New York University

Term	Definition
PBMC	Peripheral blood mononuclear cell
PGA	Physicians Global Assessment of Disease Activity
PO	per so (by mouth route of administration)
QD	qd quaque die, once daily
RA	rheumatoid arthritis
RBC	red blood cell
RF	Rheumatoid factor
SAE	serious adverse event
SC	Subcutaneous
SOP	Standard Operating Procedures
Subj	Subject
TB	Tuberculosis
TNF	tumor necrosis factor
WOCBP	women of childbearing potential

## Study Summary

Title	Rheumatoid arthritis memory B cells and Abatacept
Short Title	RAMBA
Protocol Number	IM101-768
BMS Protocol Number	IM101-768
Phase	Phase 4
Methodology	Open label
Study Duration	12 months
Study Center(s)	Single-center
Objectives	We will test the hypothesis that ABATACEPT treatment influences the levels of circulating autoimmune anti-citrullinated protein antigen (ACPA) memory B cells are central drivers of pathogenesis.
Number of Subjects	25
Diagnosis and Main Inclusion Criteria	Adults with Seropositive (CCP or ACPA) Rheumatoid Arthritis who are Naive to Biologic Disease-Modifying Antirheumatic Drugs
Study Product, Dose, Route, Regimen	Abatacept Time 0, Week 2, Month 1, 2, 3, 4, & 5 IV administration on Abatacept (7 infusions)
Duration of administration	6 months with active therapy followed by holding Abatacept for 6 months or until flare occurs while concurrent MTX or csDMARDs are continued.
Reference therapy	
Statistical Methodology	We will assess whether ABATACEPT challenge that induces clinical benefits are paralleled by reductions (i.e.,normalization) in the in vivo representation of disease-associated anti-citrullinated protein antigen (ACPA) memory B cells, and circulating autoantibody levels after 6 months of treatment.

## 1 Introduction

This document is a protocol for a human research study. This study is to be conducted according to US and international standards of Good Clinical Practice (FDA Title 21 part 312 and International Conference on Harmonization guidelines), applicable government regulations and Institutional research policies and procedures.

### 1.1 *Background*

Rheumatoid arthritis (RA) is the most common chronic inflammatory arthritis, affecting approximately 1% of the population worldwide. Women are 2 to 3 times more likely to develop the disease compared to men, with a peak incidence between the fourth and sixth decades of life. The natural history of RA is characterized by joint destruction, impaired physical function, and poor health-related quality of life. Joint erosions can be seen within 6 months of disease onset in the majority of patients, and occur more rapidly in the first year compared with later disease.

Activated T-cells are believed to play an important role in the pathogenesis of RA, especially early in the disease process, by participating in the autoimmune cascade that leads to joint inflammation and destruction. It is hypothesized that autoreactive T cells may be central to this process by producing pro-inflammatory cytokines and providing help to B cells leading to the production of autoantibodies, which in turn contribute to downstream inflammatory events, including the recruitment of neutrophils, elaboration of cytokines, such as tumor-necrosis factor (TNF)-alpha, synovitis and ultimately joint destruction.

### 1.2 *Investigational Agent*

Abatacept is a selective costimulation modulator that blocks the interaction between CD80/CD86 on antigen presenting cells and CD28 on T cells. This interaction provides a key signal necessary for full activation of T cells. By inhibiting CD28-mediated immune activation, Abatacept blocks antigen recognition and modulates the immune response to decrease T cell activation and antibody production. Therefore, Abatacept interferes with a step hypothesized to be early in the pathogenesis of RA.

Intravenously (IV) administered Abatacept was first approved in the United States (US) for the treatment of moderate to severe RA in adults in December 2005. Since then, IV Abatacept has received marketing approval for the treatment of adult RA in many other countries, including the European Union (EU), Japan, Latin America and other countries. The subcutaneous (SC) formulation was first approved in the US for the treatment of moderate to severe RA in adults in July 2011. Abatacept SC has

subsequently received marketing approval or the treatment of adult RA in the EU and other regions of the world.

### **1.3 Preclinical Data**

Not applicable

### **1.4 Clinical Data to Date**

Abatacept has been shown to be effective therapy in patients who have had inadequate responses to Methotrexate (MTX-IR) and TNF inhibitors. In the AMPLE trial Abatacept showed equivalent efficacy and safety to the TNF-inhibitor, Adalimumab.

While it is clearly resolved that continued therapy with MTX alone induces remission in ~30% of patients, the addition of Abatacept increased that to 60% in the AVERT trial. Moreover, MTX +Abatacept induced drug-free remission in up to 10% of patients for up to 6 months later.

In this challenging landscape of RA therapeutics it is unresolved whether Abatacept in addition to MTX in new onset RA can induce a remission that can be maintained with MTX alone. Drug-free remission appears unlikely with Abatacept + methotrexate, so the next step to a cure would naturally examine this question. A corollary to this question is whether this effect of Abatacept is transduced in concert with a decline in memory B cells.

The time has come to address this question for Abatacept because autoimmune memory B cells have been shown to persist at high levels during therapy with TNF-inhibitors in RA, typically given with MTX as concurrent therapy. The rate of remission on methotrexate alone was even more powerful given the fact that patients enrolled in this latter trial had previously failed methotrexate. The premise being tested (that Abatacept decreases circulating arthritogenic B cells)—is a very real possibility, given the effect of Abatacept to reduce B cell infiltration in the synovium and circulating memory B cell levels. 

### **1.5 Dose Rationale and Risk/Benefits**

Abatacept intravenous should be administered as a 30-minute intravenous infusion utilizing the weight range-based dosing specified below. Following the initial intravenous administration, an intravenous infusion should be given at 2 and 4 weeks after the first infusion and every 4 weeks thereafter for a total of 7 doses.

## **2 Study Objectives**

As a step toward a cure, we will directly assess the impact of a treatment on the underlying autoimmune disease process. Because Abatacept has unique mechanisms of action we believe that ABATACEPT treatment ameliorates RA clinical disease activity through beneficial effects on the pathologic breaches in adaptive immunity that are causal for disease. We will therefore conduct a prospective open therapeutic trial with adult seropositive (i.e., ACPA-positive) RA patients and perform intensive quantitative surveys of pathologic autoantigen-specific B cell memory.

We will test whether the clinical benefit induced by ABATACEPT treatment are paralleled by reductions (i.e., normalization) in the in vivo representation of disease-associated anti-citrullinated protein antigen (ACPA) memory B cells after 6 months of treatment. The corollary is to determine whether reductions of disease-associated memory B cells are the most meaningful marker of therapeutic response? ii) Hypothesis 2: The cessation of ABATACEPT treatment (i.e., dechallenge) with continued methotrexate therapy results in clinical flare, is then paralleled by reaccumulation in the bloodstream of disease-associated ACPA memory B cells.

### **Primary Objective**

To assess the efficacy of Abatacept + csDMARD to induce low disease activity that can be maintained on csDMARD (primarily MTX) alone. A necessary co-primary objective is the relationship between clinical response and changes in B cell and antibody parameters that are unaffected by TNF-inhibition.

To directly determine whether ABATACEPT treatment normalizes immune (i.e., B cell and antibody) abnormalities associated with seropositive RA over time and assess for correlations with clinical response measures. The investigations will include: i). Direct quantitation of the frequency of circulating ACPA-bearing memory B cells (2); ii) Flow cytometric determinations of effects on B-cell subsets, to determine whether ABATACEPT normalizes disease-associated increases in activated memory B cells, and the plasmablast expansions that are associated with active RA disease. iii) The effects of ABATACEPT on circulating IgM-, IgG- and IgG-ACPA antibody levels, in assays using a panel of matched citrulline- and arginine-containing peptides/self-proteins. iv) Serum will be collected for cytokine/chemokine profiling, which will be highly informative due to the challenge/dechallenge design.

### **Secondary Objective**

We will correlate the relationships between co-primary endpoints over time and then confirm this relationship by dechallenge of Abatacept after induction of low disease activity at 24 weeks.

We will assess whether ABATACEPT therapy that induces clinical benefits, are paralleled by reductions (i.e., normalization) in the in vivo representation of disease-associated anti-citrullinated protein antigen (ACPA) memory B cells after 6 months of

[figure not shown]
treatment. This can be confirmed by dechallenge experiments in the approximately 70-80% we expect to be in low-disease activity at this time point. While MTX therapy will be maintained, little or no effect of MTX on memory B cell formation is expected as seen in Juvenile Idiopathic Arthritis.

### 3 Study Design

#### 3.1 General Design

A phase IV open-label clinical trial in which each CCP/ACPA+ patient will be their own longitudinal control for the immunomodulatory activity of Abatacept. All patients will have blood collection, including for peripheral blood mononuclear cells (PBMC), PBMC RNA and plasma, at screening and at day 0 after which Abatacept will be initiated in concert with methotrexate or pre-existing csDMARD. Each patient will then be reevaluated at 3 months and 6 months. In all patients, Abatacept will be discontinued after 6 months. Patients who have flared or failed to achieve low disease activity at 6 months, will exit the trial except for one post study visit for lab work at 9 months.

In patients who have achieved low disease activity by DAS28-CRP (<3.2) or CDAI (<10), Abatacept will be held for 6 months or until a flare results. A flare is defined by an examination demonstrating a DAS28-CRP that is greater than an absolute value of 4.0) or a CDAI >15, both defining the mid-range of a moderate flare. Alternatively, a 30% increase in the absolute level of the DAS28-CRP or CDAI that result in measures of 3.2 and 10 respectively, will be considered evidence of a flare. If patients do not experience a flare after 6 months off Abatacept (by week 52) they will also exit the study after a final visit with an exit blood draw.

Overall, in this pilot study, patient screening will continue until 25 suitable patients are enrolled and started on therapy in the trial. We predict enrollment of 2-3 patients/month, and hence the study should be fully enrolled by month 14 with the expectation that 70-80% will achieve low disease activity at week 24 enabling 17-20

patients to be followed for flare following Abatacept dechallenge. This estimate is based on the observation that treat provides nearly 60% ACR 50 responses, despite the fact that patients were selected for evidence of erosive disease.

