**REMISSION OR LOW DISEASE ACTIVITY TABLE OF EVENTS WITH FLARE**

Procedure	Screening Period	DAY 1	WEEK 2	MONTH 1,2,3,4,5	MONTH 6/ET	FLARE	EVERY 4 WEEKS	FOLLOW-UP (WEEK 48-52)
Medication review	X	X	X	X		X	X	X
Review of side effects	X	X				X		
Physical examination	X	X			X	X		
Height (screening only) & weight	X	X		X	X	X	X	
Blood sample(s) (Approx.166-176 - ml, or - 12 tablespoons per visit )	X	X		X	X	X	X	
Urine sample	X	X		X	X	X	X	
Pregnancy test for women who can become pregnant	X	X		X	X	X	X	
Vital signs (temperature, blood pressure, heart rate (pulse))	X	X		X	X	X	X	
Assessments of your tender and swollen joints	X	X		X	X	X	X	
Assessments of disease activity	X	X		X	X	X	X	
Your Assessment of pain	X	X		X	X	X	X	
Rapid 3 patient questionnaire	X	X		X	X	X	X	
Abatacept infusion		X	X	X		X	X	
Adverse events		X		X	X	X	X	X

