**REMISSION OR LOW DISEASE ACTIVITY TABLE OF EVENTS**

Procedure	Screening Period	DAY 1	WEEK 2	MONTH 1, 2, 3,4,5	MONTH 6/ET	MONTH 9	FOLLOW-UP (WEEK 48-52)
Medication review	X	X	X			X	X
Review of side effects	X	X					
Physical examination	X	X			X		
Height (screening only) & weight	X	X	X	X	X		
Blood sample(s) (Approx.166-176 - ml, or - 12tablespoons per visit)	X	X	X	X	X	X	
Urine sample	X	X	X	X	X		
Pregnancy test for women who can become pregnant	X	X	X	X			
Vital signs (temperature, blood pressure, heart rate (pulse))	X	X	X	X	X		
Assessments of your tender and swollen joints	X	X	X	X	X	X	
Assessments of disease activity	X	X	X	X	X	X	
Your Assessment of pain	X	X	X	X	X	X	
Rapid 3 patient questionnaire	X	X	X	X	X		
Abatacept infusion		X	X	X			
Adverse events		X		X	X	X	X

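### The flare schedule ticks Abatacept infusions after Month 6 against a stated total of 7 and discontinuation in all patients, and section 6.2 does not separate samples taken before and after re-exposure

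*Combined protocol and SAP*

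**What the plan says.** Three places in the text describe a fixed course. The Study Summary lists Time 0, Week 2 and Months 1 to 5 and counts 7 infusions. Section 1.5 gives infusions at 0, 2 and 4 weeks and "every 4 weeks thereafter for a total of 7 doses". Section 3.1 adds "In all patients, Abatacept will be discontinued after 6 months".

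For patients in low disease activity, the Study Summary describes active therapy "followed by holding Abatacept for 6 months or until flare occurs", and section 3.1 says "Abatacept will be held for 6 months or until a flare results". Neither says what happens to the drug after the flare.

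Section 5.1 repeats the four-weekly regimen without a total. The paragraph on dose modifications in the absence of adverse events then refers back to that regimen.

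The table headed "REMISSION OR LOW DISEASE ACTIVITY TABLE OF EVENTS WITH FLARE" ticks infusion at Day 1, Week 2 and Months 1 to 5, leaves it blank at Month 6/ET, and ticks it again at FLARE and EVERY 4 WEEKS. Blood samples are ticked in the same two columns. The non-responder table and the low-disease-activity table without flare tick no infusion after Month 5.

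Section 6.2 plans Spearman correlations and paired t tests of longitudinal measurements. It names no time points and no exposure status. Section 6.3 analyses all treated subjects.

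**The concern.** Staff who follow the text and staff who follow the flare table would act differently on whether a patient who flares receives more study drug. A protocol should not leave that open, even in a single-centre pilot.

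There is also an analysis consequence. Hypothesis 2 in section 2 says that stopping Abatacept leads to flare, paralleled by re-accumulation of ACPA memory B cells. Section 3.3 makes the withdrawal phase the step that confirms the relationship. If Abatacept is restarted at flare, blood taken afterwards no longer reflects withdrawal. Nothing in section 6.2 keeps such samples out of the comparison, where they could weaken a re-accumulation signal.

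**Working it through.** **1. The plan's own total.** Inputs: the Study Summary time points and the section 1.5 spacing.
- By visit: 1 (Time 0) + 1 (Week 2) + 5 (Months 1 to 5) = 7.
- By week: 0, 2, 4, 8, 12, 16, 20 = 7 infusions, the last at week 20.

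The stated 7 is reproduced.

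**2. The flare table as printed.** Months 1 to 5 again give 7 in total. The tick at FLARE adds 1, and each EVERY 4 WEEKS visit after it adds 1 more.
- Minimum for a patient who had all 7 and then flares during the hold: 7 + 1 = 8.
- Maximum: not fixed, because no end date is given for the four-weekly infusions.
- Illustration only, assuming a flare at week F, a last infusion no later than week L, and none at the week 48-52 follow-up: extra infusions = 1 + (L - F)/4, for F and L on the four-week grid. F = 28, L = 48 gives 1 + 5 = 6, total 13. F = 28, L = 44 gives 1 + 4 = 5, total 12. F = L gives 1, total 8. The range is 8 to 13. The conclusion uses only the minimum of 8.

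**3. The possible readings side by side.**
- Restart at flare: the 7-infusion total and the discontinuation in all patients are then untrue for patients who flare.
- EVERY 4 WEEKS means visits during the hold, before any flare: the tick then contradicts the hold itself.
- The ticks are clerical: the table is then wrong. In all 14 rows, EVERY 4 WEEKS has the same entry as the Months 1 to 5 column, so carry-over from that column cannot be excluded.

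Each reading leaves a stated rule or a printed tick wrong.

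**4. Patients affected.** Section 3.1 expects 70-80% of 25 in low disease activity at week 24: 0.70 x 25 = 17.5 and 0.80 x 25 = 20, given there as 17-20. That is an expectation; the maximum is the 25 enrolled. No flare rate is stated, so the number who would meet the extra ticks cannot be computed.

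**5. Samples affected.** The flare table has two blood columns after Month 6, and both carry an infusion tick. On the restart reading, a four-weekly sample after flare follows a re-infusion. The FLARE sample precedes re-exposure only if it is drawn first. Section 3.1 gives the order of blood and drug at the start of treatment, "at screening and at day 0 after which Abatacept will be initiated", but not at flare. The documents give no effect size or standard deviation for the B cell measures, so any dilution cannot be calculated.

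**The case against.** The strongest defence is that the documents can be read coherently: a 7-infusion course, a hold that ends at flare, and a separate schedule from flare onward, with visits set out to weeks 48-52. On that view the protocol under-describes a phase rather than contradicting itself. This has force, and a restart is a plausible reading. It still leaves the section 1.5 total and the section 3.1 statement about all patients wrong for those who flare. Section 3.1 also describes exit for Month 6 failures and for patients who never flare, but has no sentence for those who flare during the hold.

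A second defence is that a restart may be described in material not available here: the figure under Secondary Objective, or the consent form. That is possible. Even so, the Study Summary, sections 1.5 and 3.1 and the flare table would still disagree.

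Third, section 6.2 is brief throughout, as suits an exploratory pilot, and Month 6 against the flare sample is the natural contrast for Hypothesis 2. This also stands: the missing sample rule is one part of a wider gap, and alone would be a smaller matter.

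A reader might infer that the ticks prove a planned restart, because weight and pregnancy test are ticked after Month 6 only in the flare table. The documents do not support that. Urine, vital signs and Rapid 3 follow the same pattern. Weight and pregnancy test are also ticked at Month 6/ET in that table, where infusion is blank.

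**Conclusion.** The inconsistency is real and should be resolved. Followed as printed, the flare table gives a patient who flares at least 8 infusions against the stated 7, assuming the first 7 were all given. The number of such patients is unknown: 17 to 20 are expected to enter the withdrawal phase, and 25 is the maximum. The risk to the analysis depends on the restart reading and is confined to Hypothesis 2 and the secondary dechallenge endpoint. Its size cannot be computed.

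Two stronger conclusions might be drawn, and the documents support neither. One is that the clinical outcome on csDMARD alone is contaminated; for a patient who flares, that outcome is settled at the flare, before any re-infusion. The other is that safety or contraception periods become undefined. The adverse event and contraception periods in sections 7.1 and 4.1 run from the last administration or treatment completion and simply move with any later dose. Adverse events are also scheduled for collection to weeks 48-52 in all three tables.

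**What to change.** 1. Reconcile the Study Summary, sections 1.5, 3.1 and 5.1, and the flare table, so that they agree on whether infusions occur after Month 6, on the total number, and on what happens to patients who flare during the hold. This review takes no position on which version is right.

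2. State in section 6.2 that the dechallenge comparison uses only post-Month-6 samples drawn before any re-exposure to Abatacept. The flare sample counts if it is drawn before any infusion that day. Report time since last infusion for each sample, and summarise any later samples separately.

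The cost is a protocol clarification and one sample rule, with no new visits, samples or patients. The downside is slightly fewer samples in the dechallenge comparison.

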### 3.2 Primary Study Endpoints

To assess the efficacy of Abatacept + csDMARD to induce low disease activity [DAS28-CRP (<3.2) or CDAI (<10) that can be maintained on csDMARD alone. A necessary co-primary objective is the relationship between clinical response and changes in B cell and antibody parameters that are unaffected by TNF-inhibition.

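### A patient can enter the abatacept hold on one disease-activity index and be called flared on the other, which was never low, after almost no change

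*Combined protocol and SAP*

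**What the plan says.** All of the relevant rules are in section 3.1 (General Design), and section 3.2 repeats the low disease activity (LDA) cut-offs.

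- Entry to the hold: "In patients who have achieved low disease activity by DAS28-CRP (<3.2) or CDAI (<10), Abatacept will be held for 6 months". The sentence goes on to end the hold early if a flare occurs.
- Flare, absolute limb: "A flare is defined by an examination demonstrating a DAS28-CRP that is greater than an absolute value of 4.0) or a CDAI >15".
- Flare, relative limb: "a 30% increase in the absolute level of the DAS28-CRP or CDAI that result in measures of 3.2 and 10 respectively". No reference visit is given for the 30%.
- Exit at Month 6: "Patients who have flared or failed to achieve low disease activity at 6 months, will exit the trial", apart from one laboratory visit at Month 9.
- Drug at Month 6: "In all patients, Abatacept will be discontinued after 6 months".
- End of the hold: "If patients do not experience a flare after 6 months off Abatacept (by week 52) they will also exit the study".
- Expected numbers: "the expectation that 70-80% will achieve low disease activity at week 24 enabling 17-20" patients to be followed.
- Primary endpoint, section 3.2: to "induce low disease activity [DAS28-CRP (<3.2) or CDAI (<10) that can be maintained on csDMARD alone".

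Every clinical rule is met on either index. Neither sections 3.1 to 3.3, the event tables nor section 6 requires the index that signals flare to be the one on which the patient was low.

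**The concern.** Within one index, the protocol leaves a gap between the LDA cut-off and the absolute flare cut-off: 15 − 10 = 5 CDAI points, or 4.0 − 3.2 = 0.8 DAS28-CRP units. That gap is what makes a flare mean a real loss of the response. It works only if both cut-offs are read on the same index. A patient who enters the hold on DAS28-CRP alone may have a CDAI anywhere from 10 to 15 at Month 6, so part or nearly all of the gap is already used up on the day abatacept stops. The same holds the other way round for a patient who enters on CDAI alone with a DAS28-CRP between 3.2 and 4.0.

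Two parts of the study depend on the flare label. The primary endpoint is LDA that lasts on csDMARD alone. Hypothesis 2 (section 2) expects flare after withdrawal to be paralleled by a return of ACPA memory B cells. A flare recorded with almost no clinical change lowers the apparent durability of response and also weakens the biological contrast that the withdrawal phase is meant to show.

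**Working it through.** **Inputs.** The LDA and flare cut-offs and the 30% rule come from section 3.1, as do the 25 patients and the expected 70-80% in LDA. Two assumptions are mine: the 30% rise is measured from the Month-6 value, and the relative limb means reaching at least 3.2 or 10.

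**The plan's own figure.** 25 × 0.70 = 17.5 and 25 × 0.80 = 20.0, which agrees with the stated 17-20.

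**Rise needed on an index that was low at Month 6.** For a value c below 10, CDAI flares at the lower of two levels: just above 15, or the larger of 10 and 1.3c. The smallest rise occurs where 1.3c = 10, so c = 10/1.3 = 7.69 and the rise is 10 − 7.69 = 2.31. For DAS28-CRP, d = 3.2/1.3 = 2.46 and the rise is 3.2 − 2.46 = 0.74. At the top of the LDA range the DAS28-CRP rise is 4.0 − 3.2 = 0.8, so 0.74 is the minimum.

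**Rise needed on an index that was not low.** The floors of 10 and 3.2 are already passed and no longer protect, so the rise is min(15, 1.3c) − c for CDAI and min(4.0, 1.3d) − d for DAS28-CRP. The absolute limb needs a value just above its cut-off.

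| CDAI at Month 6 | Rise to flare | DAS28-CRP at Month 6 | Rise to flare |
|---|---|---|---|
| 10 | 3.0 | 3.2 | 0.8 |
| 11 | 3.3 | 3.26 | 0.74 |
| 12 | 3.0 | 3.5 | 0.5 |
| 12.69 | 2.31 | 3.8 | 0.2 |
| 14 | 1.0 | 3.9 | 0.1 |
| 14.5 | 0.5 | | |

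The rise falls below the minimum for a low index once the Month-6 value exceeds 15 − 2.31 = 12.69 (CDAI) or 4.0 − 0.74 = 3.26 (DAS28-CRP). It approaches zero at 15 and 4.0.

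**Can such a patient exist?** The documents print no index formulas, so this is a feasibility check only, on the usual ones: DAS28-CRP = 0.56√TJC + 0.28√SJC + 0.36 ln(CRP + 1) + 0.014 × patient global (0-100) + 0.96; CDAI = tender joints (TJC) + swollen joints (SJC) + patient global + physician global (each 0-10). With 1 tender and 4 swollen joints, CRP 1 mg/L and patient global 5, DAS28-CRP = 0.56 + 0.56 + 0.25 + 0.70 + 0.96 = 3.03. Physician global 4 gives CDAI 14. Raising it to 6 gives CDAI 16, which is a flare, while DAS28-CRP stays at 3.03. The rule-based result above does not depend on these formulas.

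**Weight of one patient.** One of 20 is 5.0% and one of 17 is 5.9% of those held. This is the weight of any single reclassified patient, not an estimate of the total effect.

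**LDA and flare on one index.** DAS28-CRP going from 3.1 to 3.9 is no longer below 3.2, but it is not a flare either: 3.9 is below 4.0 and below 1.3 × 3.1 = 4.03. No flare and still in LDA are therefore different outcomes even when only one index is used.

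**The case against.** The best defence is that an either-index trigger is a legitimate choice. The absolute limb is a state threshold that the protocol places in the middle of moderate activity, and it is meant to fire there whatever the size of the change. Any cut-off can be crossed by a small step. This stands as a reason to keep the either-index rule as a clinical alert. It does not justify using that rule for an endpoint about losing a response, because the patient had no response to lose on that index.

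A reader might infer four stronger points that the documents do not support.

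- *A discordant patient at Month 6 meets both the hold and the exit rule with no way to decide.* The exit sentence covers anyone who has flared, whether or not LDA was also met, and the hold ends when a flare occurs. Flare therefore already takes precedence by implication, and abatacept stops in all patients anyway.
- *Sections 3.1 and 3.2 contradict each other.* Section 3.2 does not define what maintained means. A contradiction appears only if it is read as either index still low.
- *The results shift by a known amount.* No rate of disagreement is given, and section 6.2 does not explicitly plan a flare-free rate.
- *The responder t-test is distorted.* Section 6.2 does not define responder and does not tie it to flare status.

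**Conclusion.** The concern holds for the hold period. As written, a patient can be declared flared on an index that was never low, after a rise that approaches zero, while still in LDA on the index that admitted them to the hold. The same label on an index that was low needs at least 2.31 CDAI points or 0.74 DAS28-CRP units. These minima rest on Month 6 as the reference for the 30% rise, which is the natural choice but is not stated.

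The number of patients affected cannot be computed from the documents. Section 6.1 gives no sample size calculation, and section 6.2 calls the work exploratory and preparatory to power analyses for larger studies. That limits the harm, but a withdrawal event carried into later planning should be defined so that others can reproduce it. Priority is minor to moderate.

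**What to change.** Amend sections 3.1 and 3.2, ideally before the first Month-6 visit:

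1. For the study endpoint, judge flare on the index on which the patient qualified for the hold. Name the governing index for patients low on both.
2. Take the 30% rise from the Month-6 value, to at least 3.2 or 10.
3. Confirm in one sentence that a patient who meets flare criteria at Month 6 exits, as the wording already implies.
4. State whether maintained means no flare or still below the LDA cut-off.
5. Compute both indices at each hold visit and at the week-52 final visit. Report which index and which limb signalled each flare, and give the either-index flare rule as a sensitivity analysis.

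The cost is mostly wording. Section 4.1 asks for only one index at screening, and the event tables list a general disease-activity item without naming an index or CRP. Joint counts and blood are already scheduled, so making both indices computable should be a small addition. The tables show disease activity at Month 6, and then at Month 9 or at flare and every 4 weeks, but none shows it at Week 48-52. It has to be added there.

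There are two downsides. The flare-free rate will mix two indices. A worsening seen only on the other index would be managed clinically but not counted as an endpoint flare. If abatacept is restarted for such a worsening, the patient is no longer on csDMARD alone, so the restart should be recorded and its handling stated.
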